## PROTOCOL TITLE: Videoconferencing for Remote Assessment of Physical Performance

instructions, starts, stops, and times test using a standard stopwatch). The other investigator will be at the participant's home to observe and time the tests. The videoconferencing software records the assessments for later viewing and scoring (i.e., timing via stopwatch). One-month later, the investigator who performed the videoconferencing assessment will watch the video recording and re-score the tests to determine intra-rater reliability. At least 3 different investigators will watch the video recordings and score the tests (using a stopwatch) to determine inter-rater reliability. All investigators will receive specific training in how to time the performance tests.

For Phase 3, individuals who provided consent to re-contact will be invited to repeat the study, only this time, without a direct observer in their home. Since these participants will have already completed the study, we anticipate the test instructions should be sufficient for the participants to safely self-administer the two physical performance tests in their own home, while only communicating with the remote assessor (located at UNM). Otherwise, further improvements/clarifications to the test instructions will be made.

For Phase 4, newly enrolled participants will complete the study as in Phase 3. Phase 4 eliminates the practice effect among the participants repeating the study in Phase 3.

\*\*A copy of the video instructions for the study participant has been uploaded as a supporting document. The video is also available on YouTube via this private link: <https://youtu.be/k5bHRnjNcuo>.

Participants will wear an activity monitor during their physical performance test. The ActivPAL3 activity monitor is a small device (2.4 x 4.3 x 0.5 cm; 10g) that will be attached to the anterior midline of the thigh using a PALStickie™ (a double-sided hypoallergenic sticky pad) or Tegaderm Dressing (a transparent dressing/tape). The ActivPAL3 provides time-stamped data (sitting, standing, and stepping) that will be used to further assess the validity and reliability of the videoconferencing method to assess physical performance.

**This is not a device study, i.e., this study does not evaluate the efficacy or safety of a device. There is no information on the FDA website regarding the activPAL3 monitor (NOTE: these monitors are from a company in Scotland, UK). However, these monitors are similar to the ActiGraph monitors except for the attachment method. The activPAL3 monitors are not investigational devices as they are commercially available (<http://www.paltechnologies.com/>); the shipment of activPAL3 monitors was cleared by the FDA and delivered to the Study PI. These monitors are the gold standard for objectively measuring sedentary behavior and ambulation in research study participants and have been used in many trials in the U.S. As with ActiGraph monitors, activPAL3 monitors are more expensive than consumer wearable monitors (e.g., FitBit, Jawbone) and require special software to analyze the data, thus these monitors are used in research rather than being purchased by consumers. In this study, the monitors are used to measure outcomes (frequency, duration, and intensity of free-living sedentary behavior and light physical activity), and are not used to diagnosis or treat disease, or to support/sustain life.**

**These monitors do not present a potential for serious risk to the health, safety, or welfare of the subject. There is a potential for a small risk of skin irritation due to the adhesive**

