### 1.0 Objectives

#### .1 Primary Objectives and Hypotheses

- 1.1.a The primary objective is to evaluate the validity and reliability of using videoconferencing to assess physical performance tests self-administered by older cancer survivors in their own homes. This remote assessment will be compared to the traditional face-to-face (i.e., in-person) assessment and to accelerometer (activPAL) data.
- 1.1.b We hypothesize that older cancer survivors, in the presence of a family member or friend, will be able to successfully complete the physical performance self-assessment in the home environment.
- 1.1.c We further hypothesize that the results (time to complete performance tests in seconds) between the videoconferencing method and the traditional face-to-face method will be within a clinically acceptable limit (intra-class correlation coefficient (ICC)  $\geq .80$ ).

The ultimate goal of this research study is to develop a test protocol to allow older cancer survivors to self-administer physical performance tests in their own home, while an investigator remotely assesses the tests via videoconferencing. The test protocol includes written and video instructions and the test kit (tablet, tablet stand, measurement tools). To achieve this objective, we will proceed with a series of phases. We will apply a similar concept of “saturation” as is done in qualitative studies. In qualitative studies, the number of focus groups or interviews is based on the saturation point, i.e., the point at which no new information is learned. For the current study, we propose to include a range of participants at each study phase. At the point at which no new information is being learned, i.e., no further adjustments are needed to the test protocol, we will proceed to the next phase.\*\*

Phase 1: First, we will test proof-of-concept that participants will be able to follow the testing protocol and use the tablet PC to communicate with the investigator (10-12 participants). The test protocol will be refined based on what is learned after a minimum of 10 participants. We anticipate no more than 12 participants needed for this phase.

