### *Analyses*

The validity of the videoconference assessment will be evaluated using the limits of agreement statistic, which is the range within which 95% of differences between measurements obtained by 2 methods will lie. The videoconference assessment will be considered valid if the limits of agreement are within a clinically acceptable limit. This limit will be determined *a priori* through discussions between the PI and her mentoring team. Intraclass Correlation Coefficients (ICC) will be used to examine intra-rater and inter-rater reliability of the videoconference assessment of physical performance. Interpretation of ICC values is as follows: 0.75-1.00 = excellent reliability; 0.60-0.74 = good reliability; 0.40-0.59 = fair reliability; and <0.40 = poor reliability.

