## PROTOCOL TITLE: Videoconferencing for Remote Assessment of Physical Performance

- Videoconferencing files will be downloaded from the tablet and stored on a secure computer server. The files will be password protected and the file name will not include any identifying information (e.g., study ID number rather than participant's name). These video files will be saved in a limited-access (only key personnel) folder on the secure server for up to 3 years upon completion of the validation study. This time will allow for publication of the study results and to allow the PI to retrieve any additional information to inform the remote assessment for the future intervention trial, if needed.
- After downloading the videoconferencing files, each android tablet will be restored to factory settings to remove all data and settings prior to being used by the next study participant.
- Study staff are required to have completed training for the responsible conduct of research.

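### The intra-rater ICC mixes live with replay scoring and the inter-rater ICC uses recordings only, yet both are labelled as reliability of the videoconference assessment

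*Combined protocol and SAP*

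**What the plan says.** The primary objective (1.1.a) is to "evaluate the validity and reliability of using videoconferencing to assess physical performance tests self-administered by older cancer survivors". Under Study Design in section 9.0, the remote investigator works over the live link and provides "instructions, starts, stops, and times test using a standard stopwatch". A colleague in the room times the same performance, and the session is recorded.

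Two reliability exercises follow from the recording:

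- Intra-rater: one month later, the remote investigator from the live session "will watch the video recording and re-score the tests to determine intra-rater reliability". Section 17.0 repeats this step.
- Inter-rater: "At least 3 different investigators will watch the video recordings and score the tests (using a stopwatch) to determine inter-rater reliability". No second live remote assessor is described. Nothing says that the live score joins this set.

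The endpoint section (8.1.b) and the Analyses part of section 10.0 both state that ICCs "will be used to examine intra-rater and inter-rater reliability of the videoconference assessment of physical performance". Neither limits this to recorded video, and neither gives the form of the ICC (absolute agreement or consistency). On the source of the recording, section 10.0 (Maintaining Confidentiality) says only: "Videoconferencing files will be downloaded from the tablet and stored on a secure computer server".

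**The concern.** The method is meant for live use. The ultimate goal in section 1.0 is remote assessment by videoconference, Phases 3 and 4 have only a remote assessor, and a later intervention trial may adopt the method. Readers will take an ICC for the videoconference assessment as describing that use.

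The planned data answer different questions. In the intra-rater pair the rater stays the same, but the viewing occasion and the mode of scoring change together. Rater repeatability therefore cannot be separated from the move from live to replay. In the inter-rater set, everyone scores the same file. These scorers do not instruct, start or stop the participant, and they all see the same picture and sound. Their ICC cannot respond to differences in how live assessors cue and time the test, or to error that arises only on a live link. This applies to the chair stand as well as the Timed Up & Go (TUG), because the live assessor's calls to start and stop are already fixed in the recording.

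At stake is a reliability claim, part of the primary objective, that is wider than its evidence.

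**Working it through.** The plan states no reliability figure, SD, ICC form or precision target, so there is nothing to reproduce. The check below shows what each design estimates. All SDs are assumptions for TUG time in seconds.

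**Inputs.** p = between-participant variance (SD 1.5, 2.5 or 4 s). r = replay error variance (SD 0.2 s, so r = 0.04). L = live error variance = r + live-only variance (live-only SD 0, 0.3 or 1.0 s). Errors are taken as independent.

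**Single-score ICCs with no offset**

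- Live-live, the quantity the label implies: p / (p + L)
- Live-replay, the planned intra-rater pair: p / (p + (L + r)/2)
- Replay-replay, the planned inter-rater set: p / (p + r)

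**Worked case.** With p = 2.5² = 6.25 and live-only SD 1.0 s, L = 0.04 + 1.00 = 1.04.

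- Live-live: 6.25/7.29 = 0.857
- Live-replay: 6.25/(6.25 + 0.54) = 0.920
- Replay-replay: 6.25/6.29 = 0.994

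| Between SD (s) | Live-only SD (s) | Live-live | Live-replay | Replay-replay |
|---|---|---|---|---|
| 1.5 | 0 | 0.983 | 0.983 | 0.983 |
| 1.5 | 0.3 | 0.945 | 0.964 | 0.983 |
| 1.5 | 1.0 | 0.684 | 0.806 | 0.983 |
| 2.5 | 0 | 0.994 | 0.994 | 0.994 |
| 2.5 | 0.3 | 0.980 | 0.987 | 0.994 |
| 2.5 | 1.0 | 0.857 | 0.920 | 0.994 |
| 4.0 | 0.3 | 0.992 | 0.995 | 0.998 |
| 4.0 | 1.0 | 0.939 | 0.967 | 0.998 |

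The last column does not move with live-only error. The live-replay column carries half of the live-only variance. The three ICCs agree only when live scoring adds nothing.

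**Constant offset.** Suppose live times differ from replay times by a fixed b. An absolute-agreement ICC gains b²/2 in its denominator; a consistency ICC does not change. With b = 0.5 s, b²/2 = 0.125. In the worked case the live-replay ICC falls to 6.25/6.915 = 0.904 under absolute agreement and stays at 0.920 under consistency.

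The absolute-agreement live-replay ICC drops below live-live when (L + r)/2 + b²/2 > L, that is, when b² exceeds the live-only variance. For example, with between SD 1.5 s, live-only SD 0.3 s and b = 0.5 s, it is 2.25/(2.25 + 0.085 + 0.125) = 0.915, against 0.945 live-live.

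**The case against.** The best defence is that a recording is the practicable second reading. One person cannot score the same performance live twice, and section 9.0 deliberately avoids repeat performances because of learning and fatigue. The plan also says openly how each score is obtained. This stands: the fault lies in the label and the missing separate analysis, not in using recordings.

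A second defence is that live error is examined elsewhere. Simultaneous remote and in-room timing captures it in the limits of agreement, technology problems are tracked (8.1.a), and activPAL gives time-stamped data. These help with validity, but they do not fill the gap. The simultaneous pair mixes rater with method. Section 4.0 calls Phase 3 the reliability phase, but it brings in participant change and practice effect and has no stated reliability analysis. No reliability analysis is given for activPAL either.

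Third, the size rests on assumed SDs, and small live-only error makes little difference (0.980 against 0.994 at 2.5 s and 0.3 s). That is fair, and the documents cannot settle it.

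A reader might also infer four stronger points that the documents do not support:

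- That neither ICC carries any information on live scoring. The intra-rater pair contains one live score and so carries part of the live error.
- That the intra-rater ICC is too pessimistic. Against live-live reliability, this needs an absolute-agreement form and an offset larger than the live-only SD. The plan specifies neither.
- That the .80 criterion is threatened. In 1.1.c that criterion is for videoconference against face-to-face, not for rater reliability.
- That the recordings hide link delay because they come from the tablet. Section 10.0 says where the files are downloaded from, not which stream they hold.

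**Conclusion.** The point holds as one about what is estimated and how it is labelled. The planned intra-rater ICC is same-rater live-versus-replay agreement. The planned inter-rater ICC is reliability of scoring recorded video. Neither is the reliability of live videoconference assessment that sections 8.1.b and 10.0 imply.

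If live random error exceeds replay error and there is no constant offset, both overstate live reliability, the inter-rater ICC most. With an offset, the direction for the intra-rater ICC depends on the ICC form, which the plan leaves open.

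The size is unknown. Across the assumed values above, the inter-rater ICC exceeds live-live by nothing (no live-only error) up to 0.983 against 0.684. In that last case, live reliability would be good on the plan's own scale (0.60-0.74), while both planned ICCs (0.806 and 0.983) would read as excellent (0.75-1.00). A live-only SD of 1.0 s is an illustration, not an estimate. The illustration covers TUG times only; for the chair-stand count the argument is qualitative.

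**What to change.** 1. Keep the live-versus-replay pair, but analyse and report it as same-rater live-versus-replay agreement. Give the mean live-minus-replay difference, its limits of agreement and an absolute-agreement ICC.
2. Name the inter-rater ICC as reliability of scoring recorded video. Limit that conclusion to recorded scoring, not live assessment.
3. Optionally, add one second replay viewing by the same investigator, masked to earlier scores. Replay against replay would then separate rater repeatability from the mode effect. This should be an addition: as a replacement it would remove the only live score from the reliability data.
4. State which stream the recording holds, so that readers know whether replay scorers saw what the live assessor saw.

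Items 1, 2 and 4 need only wording and analysis of scores already planned. Item 3 costs one more viewing of 10-20 short recordings. The real price is a narrower reliability claim.

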## PROTOCOL TITLE: Videoconferencing for Remote Assessment of Physical Performance

**used to attach the activPAL3 to the thigh. However, if irritation occurs, it usually occurs after several hours or days of use. The participant will only be wearing the monitor for approximately one hour.**

### *Physical Performance Test*

The physical performance tests include the 30-second chair stand test (30s-CST) and the Timed Up & Go (TUG) test. The TUG test is measured as the time to stand from a standard arm chair, walk 10 feet, turn around, return to start and sit down. The TUG test is a measure of mobility and balance, has good validity [ $0.6 < r < 0.85$ ] and excellent reliability. The 30s-CST is measured as the number of times a person comes to a full standing position from a chair in 30 seconds, as quickly as possible, without using ones' hands. The 30s-CST is a measure of lower extremity strength and dynamic balance, has excellent reliability [ $ICC=0.84-0.92$ ]. These two performance tests incorporate movements typically undertaken during normal daily activities, and thus represent tests that are more likely to be safely performed in a clinically unsupervised setting. Both of these tests are included in the CDC Stopping Elderly Accidents, Deaths, & Injuries (STEADI) toolkit for assessment of falls. Note that a friend or family member will be present during the test, with the requirement of being physically capable of providing support if needed (i.e., doesn't need a walker, wheel chair, etc.).

### **Modifications to procedures due to the COVID-19 pandemic**

We were in Phase II of this study when the NM stay-at-home order was issued and UNM entered limited operations. The home visits that had been scheduled, were cancelled. Each participant who was already enrolled, but who hadn't completed the study, provided permission to be contacted once the study resumed.

The following are steps we will take to restart this study:

- Individuals enrolled in Phase 2 will be sent a letter indicating that we are restarting the study. They will be asked if they are interested in completing the study or are no longer interested in participating (no further contact by study team). A form is available for participants to select one of these options, and return to the study team (postage paid). Since home visits are not allowed at this time, interested participants will be moved to Phase 4.
- A sample of individuals who complete Phases 1 and 2 will be invited to repeat the study in the Phase III reliability study. There are two minor modifications to this phase: a) a handout will be provided indicating our plan for minimizing risk of exposure to the novel coronavirus; and b) the toolkit (cardboard box containing tablet, stand, portable wi-fi, etc.) will be dropped off and picked up from the participant's home by a study investigator since there are only 3 toolkits and using regular mail will add further delays (4 month delay so far due to COVID-19).
- Phase 4 will proceed as planned with the following minor modifications: a) a handout will be provided indicating our plan for minimizing risk of exposure to the novel coronavirus; and b) additional recruitment method to help enroll rural participants.

Please see handout listing the safety precautions taken during the study to reduce the risk of infection from the novel coronavirus causing COVID-19 for details. Briefly, this handout

## PROTOCOL TITLE: Videoconferencing for Remote Assessment of Physical Performance

lists steps for disinfecting the toolkit contents, and ways to minimize or eliminate direct contact with a study team member.

### 10.0 Data and Specimen Management

#### *Data Management*

Data will be stored and managed using REDCap, which is a web-based electronic data capture program. It is secure and HIPAA compliant. It is available for all HSC faculty, staff, and sponsored students. Participants will also have the option of completing the surveys online through REDCap.

A REDCap database has been created to store information during the recruitment process (eligibility criteria, reasons for refusal, etc.). This is the only location where both PHI (participant name, address, phone number, email address) and the unique study ID number will be found. Only key study personnel will have access to this database.

Each participant will be assigned a unique number to identify their data. This unique number will be placed on each document (data collection form) and included in each electronic file name (saved videoconferencing file for later reviewing and scoring to assess reliability) to identify the participant.

Participants will be mailed a packet with surveys to complete before the home visit. The study investigator will collect the completed surveys at the home visit for study phases 1 & 2. For study phases 3 & 4, the participant will return the completed surveys along with the test tool kit to the study team or via mail (postage paid). Note that the surveys will only include a unique participant ID, and no identifying information. Alternatively, participants will be offered the option to complete the surveys using a secure online link to the REDCap survey database.

A data collection form will be used by the study personnel conducting the remote assessment of physical performance. This form will be identified using the unique study ID number. Data from this form will be entered into a REDCap database. Only essential study personnel will have access to this database.

All electronic files will be stored on a secure UNM Comprehensive Cancer Center server.

The NMTR will provide the following data in an Excel spreadsheet, which will be downloaded from the study team from a the NMTR secure FTP site and stored on a secure server. Of note, each NMTR case is assigned a NMTR patient ID. If a NMTR case meets the eligibility of a study, he/she is assigned a separate study ID (different than the NMTR patient ID, and it differs if he/she is eligible for more than one study). Only designated NMTR staff have access to the NMTR patient ID.

Data elements to be provided to the study team include the following: current age, age at diagnosis, year of diagnosis, cancer site, stage at diagnosis, summary treatment (yes/no): surgery, chemotherapy, radiation, hormone therapy, immunotherapy, and other therapy; and year of treatment.

## PROTOCOL TITLE: Videoconferencing for Remote Assessment of Physical Performance

\*\*NOTE: Additional data will be provided by the NMTR to characterize the non-responders. NMTR will provide the aggregate status (total count) based on their attempt to contact the patient, prior to releasing names to study staff. The status values include:

- Released, Patient actively or passively agreed to participant in this study
- Refused, Patient actively refused to participate in this study
- Do Not Contact, patient is eligible to participate but does not want to be contacted for any studies
- Bad Address, unable to contact the patient because the letter was undeliverable
- Ineligible, the patient was ineligible to participate in this study because of age, date of diagnosis, site, etc. This could happen if the patient notifies us of a discrepancy in our data. I.e. Date of birth is wrong or different diagnosis.
- Deceased, patient died prior to our attempt to contact them or prior to releasing the data to the study.

### *Analyses*

The validity of the videoconference assessment will be evaluated using the limits of agreement statistic, which is the range within which 95% of differences between measurements obtained by 2 methods will lie. The videoconference assessment will be considered valid if the limits of agreement are within a clinically acceptable limit. This limit will be determined *a priori* through discussions between the PI and her mentoring team. Intraclass Correlation Coefficients (ICC) will be used to examine intra-rater and inter-rater reliability of the videoconference assessment of physical performance. Interpretation of ICC values is as follows: 0.75-1.00 = excellent reliability; 0.60-0.74 = good reliability; 0.40-0.59 = fair reliability; and <0.40 = poor reliability.

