Phase 2: Next, 10-20 new participants will be enrolled to evaluate the validity of videoconference vs. face-to-face assessment (i.e., direct observation) of physical performance. Communication will occur between the remote assessor and the participant. The direct observer will not communicate directly to the participant, unless there is a safety issue. After completing 10 participants without a major change in the test protocol, we will proceed to the next phase.

Phase 3: This phase involves participants repeating the test protocol, but without the face-to-face assessment (i.e., direct observation). This will test the ability of the participant to receive the box of test instructions and materials in the mail or delivered by a study team member, unpack the box, communicate with the remote assessor via videoconferencing, pack up the box, and return it to the study team (postage paid) or retrieved by a study team member. This step will involve 5-10 participants from Phases 1 and 2, who have provided

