A friend, neighbor or relative is requested to be present during the assessment. This person will be able to communicate via the videoconferencing session with the investigator and must have access to a telephone should medical attention be required. However, if this person is unable to be present during the assessment once it has been scheduled, then the research investigator conducting the face-to-face assessment will cover their responsibilities. Face-to-face assessment is the traditional method for assessing these physical performance tests. We will be testing whether the remote assessment via videoconferencing can produce similar results (time in seconds to complete the tests) as the traditional (face-to-face) method.

The two different assessment methods (remote vs. face-to-face) should be within a reasonable margin of error ( $r \geq .80$ ) The two performance tests include the Timed Up & Go (TUG) Test and the 30-second chair stand test (30s-CST). The TUG test involves standing up from a standard

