## 9.0 Procedures Involved

### *Study Design*

Interested and eligible participants will be scheduled for a home visit (Phases 1 and 2). An android tablet with Wi-Fi and cellular will be used to compare videoconferencing with face-to-face assessment of 2 timed, physical performance tests. The tablet will contain videos demonstrating the performance tests, safety measures, and instructions, with features adapted for older adults (e.g., large font).\*\* Further instructions will be provided by the investigator via videoconferencing. First, we will test proof-of-concept that participants will be able to follow the testing protocol and use the tablet to communicate with the investigator (10-12 participants). While one investigator is in a different room of the house conducting the videoconference assessment, another will be in the same room to directly observe and evaluate the impediments and barriers related to the technology and test protocol. After refining the study protocol and materials, 10-20 participants will be enrolled to evaluate the validity and reliability of videoconference vs. face-to-face assessment of physical performance. The performance tests will be assessed simultaneously by two investigators to eliminate intra-participant variation that would occur with sequential assessments. A simultaneous assessment (face-to-face and remote) vs. sequential assessments avoids learning effects (among high performers) and fatigability (among low performers). One investigator will perform the assessment from a remote location using videoconferencing (provides

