### **13.0 Potential Risks to Subjects / Protection Against Risks**

This validation study poses minimal risk, since a member of the research team will be present during home visits to remotely assess physical performance (Phases 1 and 2). This research team member will be timing the participant as part of the face-to-face assessment to be compared with remote (videoconferencing) assessment. Being in the same room as the participant, this research team member will also be able to supervise the performance tests. For Phases 3 and 4, a friend, neighbor, or family member of the participant must be present during the tests. The two tests were chosen since they incorporate movements typically undertaken during normal daily activities (standing from a chair, walking a short distance, sitting on a chair), and thus represent tests that are more likely to be safely performed in a (future) unsupervised setting. Nevertheless, there are some potential risks associated with these performance tests being conducted outside of the clinic setting.

Protection against risks during the physical performance tests will include the following:

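### The verdict that videoconferencing is valid rests on estimated limits of agreement from 10 to 20 participants with no confidence intervals, so near the acceptable limit it is unreliable in both directions

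*Combined protocol and SAP*

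**What the plan says.** Section 10.0 (Analyses) gives the decision rule: "The videoconference assessment will be considered valid if the limits of agreement are within a clinically acceptable limit". Section 8.1.b states the same rule. Section 10.0 describes the limits of agreement as the range "which is the range within which 95% of differences between measurements obtained by 2 methods will lie". Neither section gives the multiplier used to calculate the limits, a confidence interval for them, or a precision target, and no other section does so.

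The acceptable limit has no number yet. Section 8.1.b has the investigator and mentoring team set it after the first 10 participants, no lower than the inter-rater difference seen under ideal conditions.

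Section 1.0 assigns the comparison to Phase 2: "10-20 new participants will be enrolled to evaluate the validity of videoconference vs. face-to-face assessment". Sections 4.0 and 9.0 agree. The phase can close at its lower end: "After completing 10 participants without a major change in the test protocol, we will proceed to the next phase". That is a rule about refining the test protocol, not about precision. The COVID-19 modifications in Section 9.0 then affect those who had enrolled in Phase 2 but not finished: "Since home visits are not allowed at this time, interested participants will be moved to Phase 4". Phase 4 has no direct observer, so these participants supply no face-to-face pair.

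**The concern.** The rule treats the calculated limits as if they were the true range of differences. With 10 to 20 pairs they are rough estimates, because each limit combines an estimated mean with about twice an estimated SD. If the true limits lie close to the acceptable limit, which side the estimates fall on is largely chance, yet the plan turns the result into a plain yes or no.

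This matters because validity is part of the primary objective (Section 1.0), and Sections 3.0 and 13.0 say that a later intervention trial may use the method. A reader of a bare verdict cannot tell a clear pass from a marginal one.

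**Working it through.** The plan gives no precision or sample-size calculation for the limits of agreement, so there is no stated figure to reproduce.

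**Inputs**
- n = 10 and n = 20: the Phase 2 range (Sections 1.0, 4.0 and 9.0).
- Rule: both estimated limits inside ±A, where A is the acceptable limit (Sections 8.1.b and 10.0).
- Assumed: normal differences, zero mean difference, limits = mean ± 1.96 SD.
- A has no number, but only the ratio r = (true limit)/A is needed. With true SD = 1, A = 1.96/r.

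**Step 1: precision of one limit.** The 95% half-width is t × SD × √(1/n + 1.96²/(2(n − 1))).
- n = 10: 2.262 × √(0.1 + 3.8416/18) = 2.262 × 0.560 = 1.27 SD, or 65% of the 1.96 SD being estimated.
- n = 20: 2.093 × √(0.05 + 3.8416/38) = 2.093 × 0.389 = 0.81 SD, or 42%.

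**Step 2: chance of a valid verdict.** This is P(|mean| + 1.96 s < A), with the mean distributed as N(0, 1/n) and s² as χ²(n − 1)/(n − 1). Numerical integration and simulation agree.

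| True limits relative to A | n = 10 | n = 20 |
|---|---|---|
| 20% narrower (r = 0.8) | 73% | 84% |
| 10% narrower (r = 0.9) | 53% | 59% |
| exactly at A (r = 1.0) | 36% | 34% |
| 10% too wide (r = 1.1) | 23% | 17% |
| 25% too wide (r = 1.25) | 11% | 5% |
| 50% too wide (r = 1.5) | 3.3% | 0.6% |

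At r = 0.9 an acceptable method therefore fails 100 − 53 = 47% or 100 − 59 = 41% of the time.

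**Step 3: sensitivity at 10% too wide.**
- With a t multiplier (2.262 or 2.093) in place of 1.96, the pass rate is 11% or 10%.
- With a mean difference of 0.5 SD and the worse true limit 10% beyond A, it is 38% or 31%.
- With a 0.5 SD mean difference added to a spread already 10% too wide, it is 12% or 4%.

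**Step 4: effect of a label.** A pass is called preliminary if |mean| + 1.96 s + half-width ≥ A.

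| True limits relative to A | Passes labelled, n = 10 | Passes labelled, n = 20 |
|---|---|---|
| 0.5 | 24% | 2% |
| 0.8 | 85% | 81% |
| 0.9 | 90% | 91% |
| 1.1 | 95% | 97% |
| 1.25 | 96% | 99% |

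**The case against.** **The rule is not lenient.** A reader might infer from the 23% and 17% that the plan readily passes poor methods. It does not. A method exactly at the limit passes only 36% or 34% of the time, and one 50% too wide almost never does. This stands: the fault is unreliability near the limit, in both directions.

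**Ten per cent beyond an unset limit may not matter clinically.** This is fair, since the limit is still to be agreed. But the plan does make it the line between valid and not valid, so the reader should see how firmly the data place the method on one side.

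**The figures do not apply to both tests.** This stands. The 30-second chair stand is a whole-number count. If its differences are only −1, 0 or +1, with 10% to 50% of pairs disagreeing (an assumption), the 10%-too-wide case passes about 17% to 38% of the time at n = 10 and 10% to 39% at n = 20. The percentages in the working are a guide for the Timed Up & Go only.

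**More pairs may be available.** Section 13.0 says of home visits in the first two phases: "This research team member will be timing the participant as part of the face-to-face assessment to be compared with remote (videoconferencing) assessment". A reader might infer that up to 12 + 20 = 32 pairs could be pooled. The documents do not plan this. The validity comparison is assigned to Phase 2, and Section 8.1.b uses the first 10 participants to inform the limit, so pooling would judge the limit partly on the data behind it. A reader might equally infer that the pandemic left fewer than 10 pairs. The documents do not say how many had been collected.

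**This is a small pilot with other evidence.** Section 3.0 uses both feasibility and pilot language, and Section 1.0 adds an ICC of at least .80 and an activPAL comparison. That argues against demanding a larger sample. It does not remove the point: the ICC criterion also has no interval, and the valid verdict is tied to the limits of agreement alone.

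**The label separates good from bad poorly near the limit.** This is true. At 0.9 of the limit it covers about nine in ten correct passes. There it correctly reports that the data cannot decide; at 0.5 it mostly disappears.

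**Conclusion.** The concern holds as a matter of precision and reporting. A yes-or-no verdict on 10 to 20 pairs, with no allowance for sampling error, is not dependable when the true limits are within roughly 10% of the acceptable limit: about one in four to one in six wrong passes on one side, and more than four in ten wrong failures on the other. By 25% too wide the wrong passes have fallen to 11% or 5%.

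The sizes rest on normal differences, zero bias and a 1.96 multiplier. A t multiplier roughly halves the wrong passes at 10% too wide, and bias can move them either way. The absence of intervals, and the half-widths of 65% and 42% of the limit being estimated, do not depend on where the acceptable limit is set. The documents do not support the stronger readings that the rule is lax, that the sample is unfit for a feasibility study, or that these rates hold for the chair stand count.

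**What to change.** In Sections 8.1.b and 10.0:

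1. For each test, report 95% confidence intervals for both limits of agreement beside the acceptable limit. The multiplier used for the limits has to be stated for this to be reproducible.
2. Describe a valid verdict as preliminary whenever an outer confidence bound lies beyond the acceptable limit.

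For the chair stand, an interval method that does not rely on normality, or the tabulated differences, should accompany the limits.

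The data and sample size stay the same; the work is a few lines of analysis. The real cost is a less definite conclusion, which also falls on acceptable methods, as the shares labelled at 0.9, 0.8 and 0.5 of the limit show. Going further, and reserving the word valid for outer bounds inside the limit, is not recommended at this size: at 0.8 of the limit the pass rate would fall from 73% to 11% at n = 10 and from 84% to 16% at n = 20.
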